5.1 Eligibility criteria

Eligible adult patients (≥ 18 years old) were identified and recruited at the participating trial site centres starting in August 2018 and ending by June 2022, 52 patients will be recruited. Participating trial centres will include the Liver and Metabolic Units at the Humanitas Gradenigo Hospital (Turin) since August 2018), and the Metabolic Unit of Dept of Medical Sciences at the Città della Salute e della Scienza hospital (Turin) since Sept 2018).

All trial participants will give informed written consent at the beginning of the screening visit prior to undergoing any tests and procedures needed to assess eligibility.

Eligibility for the trial will be determined at screening visit 1 by standard blood tests, clinical history (including written-confirmation of drug history where necessary) and physical examination to identify other illnesses or contraindications for participation.

Patients who satisfied the eligibility criteria trial at both sites will be offered to take part in a metabolic mechanistic substudy. The substudy involves a standard Oral Glucose tolerance Test (OGTT) and a standard Oral Fat Tolerance Test (OFTT) on three admissions (at least 24 hours apart from each other) and an indirect calorimetry test at the two participating centres on visits 2 (pretreatment) and 8 (4 weeks

post-treatment). A detailed summary of the metabolic substudy will be published separately. A patient's decision to partake or withdraw from the metabolic substudy will not affect their participation in the main 72-week trial.

A schematic view of trial schedule and design is presented in **Figure 1**.

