Both active treatment (phytosomal curcumin) and placebo control will be packaged and labelled with a unique identification number (in keeping with the European Unions Good Manufacturing Practice for Medicinal Product guidelines) by the manufacturer (Indena S.p.A.), to the extent that the receiving trial site will be blinded to the study drug throughout the duration of the trial. Sealed parcels (containing electronic information) will be sent with each drug package for the attention of the unblinded members of the central trial management group (TMG) nominated statistician, RG and database programmer, EP, to ensure (1) safe delivery of the correct drug and (2) blinding of the treatment allocation from the remainder of the TMG and the trial patient. Unblinding of treatment will only take place if the identity of the allocated study medication will be necessary for patient safety and care. If a serious adverse event (SAE) is deemed unexpected and possibly, probably or definitely related to phytosomal curcumin (ie, suspected unexpected serious adverse reaction=SUSAR), a clinical member of the TMG was unblinded to the medication to evaluate causality and subsequently label the event either as an unrelated SAE (for patients receiving placebo) or a SUSAR (for patients receiving phytosomal curcumin). The latter will be reported to the MHRA and the NRES, and only if patient safety is jeopardised the study medication will be discontinued and the treating clinician/patient informed.

6. Trial schedule and data collection

The trial will involve nine patient-related visits at their nearest trial site (**Figure 1**).

The study comprises four stages: (1) screening, enrollment, randomisation and baseline investigations (visits 1 and 2, over a maximum period of 14 days), (2) 504 days of study treatment (visits 3–7, over 72 weeks), (3) primary endpoint assessment including liver biopsy (visit 8, within 1 day of the EOT) and (4) post-treatment follow-up assessment (visit 9, 12 weeks after EOT). If the trial investigating team or the trial participant suspected an AE, an unscheduled visit was arranged within 24 h. Each visit included patient interview, clinical examination, anthropometry and blood/urine chemistry.

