-Improvement in anthropometry, physical activity and dietary parameters (body weight, BMI, waist circumference), physical activity and daily dietary consumption.

-Improvement in glycaemic control (fasting plasma glucose, HbA1c)

-Improvement in cardiovascular risk profile: fasting plasma lipids, oxidative stress markers, inflammatory markers/adipokines and chemokine MCP-1.

-Chronic kidney disease (CKD) regression. CKD will be defined according to Kidney Disease Improving Global Outcomes (KDIGO) guidelines as sustained (i.e., documented on 2 occasions at least 3 months apart) reduction in estimated Glomerular Filtration Rate [eGFR] <60 mL/min/1.73 m² **and/or** sustained increase in albumin excretion rate (AER) ≥30 mg/d. CKD regression will be defined as sustained (i.e., documented 3 month apart, on both follow-up visit 7 and visit 8) estimated Glomerular Filtration Rate [eGFR] ≥60 mL/min/1.73 m² **and** normalization of AER (i.e., <30 mg/d).

eGFR will be assessed from serum creatinine using the **CKD-EPI** (Chronic Kidney Disease Epidemiology Collaboration) equation, as recommended by KDIGO guidelines⁴². eGFR and AER will be classified according to KDIGO categories⁴³

-Change in absolute values of eGFR^{44, Error! Bookmark not defined.}, and of albumin excretion rate(AER).

We will estimate mean annual rates of change in eGFR from baseline to the final follow-up visit (total slopes), within each treatment allocation using linear mixed model repeated measures (MMRM);

adjustments were made for age, baseline eGFR, baseline urinary AER, diabetes, baseline fibrosis stage, systolic blood pressure, angiotensin-converting enzyme/angiotensin receptor blocker⁴⁵(see. **supplementary material**)

Exploratory outcomes

We explored the effect of treatment on Nuclear Factor(NF)-kB activation in the liver and in circulating mononuclear cell(MNCs). NF-kB is a key proinflammatory transcription factor involved in NASH development and progression and a known molecular target of curcumin (see Methods and supplementary material).

Safety outcomes

Safety end points include adverse events after the start of treatment, biochemical assessments, and clinical assessments. Selected events (including deaths, cardiovascular events, and acute pancreatitis) were adjudicated by an independent, external event-adjudication committee, whose members were unaware of the treatment assignments. A complete list of the trial end points is provided in protocol Table 1.

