Dietary record with food frequency questionnaire. Subjects will be instructed to fill in a 7-day validated and reproducible dietary questionnaire during an individual training session with a nutritionist; a list of foods is designed, for each item different portion sizes are specified according to the EPIC study⁽⁶¹⁾. The diet record was analyzed using the WinFood database (Medimatica, Teramo, Italy) according to the table of food consumption of the Italian National Institute of Nutrition and Food Composition Database for Epidemiological Study in Italy⁽⁶²⁾. Based on FFQ data, excessive alcohol use will be defined as .30 g/d for male individuals and .20 g/d for female individuals.

The FFQ will be completed at baseline (visit 1) and at end-of-treatment (visit 7). Analysis will report the change from baseline scores to the end-of-treatment .

Physical activity record.

Physical activity (PA) will be measured with the accelerometer SenseWear Armband (SWA), which had to be worn continuously on the nondominant arm for at least 3 consecutive days (2 working days and a weekend day) at baseline and at EOT. The SenseWear Armband (SWA) is a relatively new accelerometer device that can be used to quantify and monitor physical activity and energy expenditure (EE), which has been validated against indirect calorimetry⁶³ and has been shown to have acceptable reliability and reproducibility. The SWA is designed to be worn on the upper arm over the triceps. Its internal sensors include an accelerometer, a thermal flow sensor, a galvanic sensor that records skin response, a skin temperature sensor, and an air temperature sensor. The accelerometer in the armband has two axes and uses a microelectromechanical sensor that measures movement.

Physical activity is measured relative to gravity ($1\text{ mg}=9.81\text{ mm/sec}^2$) with an interval of 20 ms and categorized based on intensity, according to White et al.⁶⁴, into time spent in sedentary behavior (48 mg) and in light (48–154 mg, e.g., walking), moderate (154–389 mg, e.g., cycling), and vigorous activities (.389 mg e.g., running). The software created by the manufacturer calculates then EE using a patented algorithm that combines acceleration, heat flow, and other parameters: technical and statistical procedures have been described in detail earlier^{65, 66, 67}.

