We estimated mean annual rates of change in eGFR from baseline to the final follow-up visit (total slopes), by treatment allocation using linear mixed model repeated measures (MMRM); adjustments were made for age, sex, first baseline CKD stage, baseline eGFR; baseline urinary ACR, diabetes, history of cardiovascular disease, systolic blood pressure, angiotensin-converting enzyme/angiotensin receptor blocker use⁷⁹

Proteinuria will be estimated using measurements of urinary protein and creatinine at baseline and at baseline and at each visit thereafter.

Albuminuria and eGFR stage will be categorized according to the KDIGO classification system⁸⁰

The end-stage renal disease was defined as kidney transplantation or the receipt of dialysis for at least 30 days unless death occurred.

For exploratory outcomes, we will explore the existence of a threshold in hepatic NF-kB activation change predicting histological response (NASH resolution, fibrosis improvement) using the area under receiver operating characteristic curve (AUROC) analysis and Youden index.

A sensitivity analysis will be performed in which missing data were handled by reference-based multiple imputation informed by data from placebo recipients (see **Preplanned subgroup and sensitivity analyses suhealing**).

Safety will be analysed descriptively

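### CKD regression must be confirmed 3 months apart at visits 7 and 8, but the protocol times those visits inconsistently, and it gives the eGFR-slope analysis two different covariate lists

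*Protocol*

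**What the plan says.** **CKD regression.** Section 7 (Non liver-centered outcomes) requires eGFR of at least 60 mL/min/1.73 m² together with albumin excretion below 30 mg/d, "documented 3 month apart, on both follow-up visit 7 and visit 8".

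**Timing of visits 7 and 8.**
- Section 6 assigns visits 3 to 7 to the 72 treatment weeks and then schedules the "primary endpoint assessment including liver biopsy (visit 8, within 1 day of the EOT". Visit 9 follows 12 weeks after end of treatment.
- Section 8, on the dietary record: "The FFQ will be completed at baseline (visit 1) and at end-of-treatment (visit 7". The physical activity record uses the same label for visit 7.
- Section 5.1 schedules the metabolic substudy tests "on visits 2 (pretreatment) and 8 (4 weeks", and the sentence continues after a page break to say post-treatment.
- Section 5.4.3 refers to trial visits every 12 weeks.

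**Baseline CKD.** Section 7 defines CKD by abnormal values "documented on 2 occasions at least 3 months apart". Section 6 fits visits 1 and 2 "over a maximum period of 14 days".

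**eGFR slope.** Sections 7 and 9.2 both describe the mean annual change in eGFR from baseline to the final follow-up visit, by treatment, from a mixed model for repeated measures. Section 7: "adjustments were made for age, baseline eGFR, baseline urinary AER, diabetes, baseline fibrosis stage, systolic blood pressure", plus ACE inhibitor or receptor blocker use. Section 9.2: "adjustments were made for age, sex, first baseline CKD stage, baseline eGFR; baseline urinary ACR, diabetes, history of cardiovascular disease", plus systolic pressure and ACE inhibitor or receptor blocker use.

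**The concern.** Section 2 lists improvement of NASH-related CKD among the key secondary hypotheses. The regression endpoint depends on its confirmation interval. eGFR near 60 and albumin excretion near 30 mg/d vary from one sample to the next, and a second sample a day or a month later is a much weaker check than one 3 months later. If the visit labels are followed as some sections give them, the endpoint would be scored on pairs of values that do not meet its own definition of sustained.

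The slope analysis has a different problem. Two covariate lists for one analysis give two results, each of which the protocol supports, and nothing in the protocol says which one is reported.

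**Working it through.** **1. Visit gap**

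Inputs: treatment lasts 504 days, and 504 / 7 = 72 weeks (Section 6). Visits are every 12 weeks (Section 5.4.3). Visit 7 is end of treatment (Section 8). Visit 8 is within 1 day of end of treatment (Section 6) or 4 weeks after it (Section 5.1).

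Figure to reproduce: 3 months = 3 × 365.25 / 12 = 91.3 days, or 30.44 days per month.

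The 12-weekly grid assumes that visit 3 is the first visit after baseline, at week 12. Visit v then falls at week 12 × (v − 2), so visits 3 to 9 fall at weeks 12, 24, 36, 48, 60, 72 and 84. This agrees with Section 6, with visit 8 at end of treatment and visit 9 twelve weeks later.

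| Visit 7 | Visit 8 | Gap | In months | Nominal 3 months? |
|---|---|---|---|---|
| End of treatment (Section 8) | Within 1 day (Section 6) | at most 1 day | 1 / 30.44 = 0.03 | No |
| End of treatment (Section 8) | 4 weeks after (Section 5.1) | 28 days | 28 / 30.44 = 0.92 | No |
| Week 60 (grid) | Week 72 (Section 6) | 12 × 7 = 84 days | 84 / 30.44 = 2.76 | Yes, to visit precision |
| Week 60 (grid) | Week 76 (Section 5.1) | 16 × 7 = 112 days | 112 / 30.44 = 3.68 | Yes |

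The stated interval is reproduced only when visit 7 is at week 60, which requires setting aside the visit 7 label in Section 8. Sections 6 and 5.1 disagree about visit 8 whichever date visit 7 has.

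**2. Baseline CKD**

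Visits 1 and 2 span at most 14 days, and 14 / 30.44 = 0.46 months against the 3 required. The trial's own baseline visits cannot supply both values, so the earlier one has to predate screening. Section 5.1 mentions clinical history at visit 1 but sets no rule for earlier eGFR or albumin values.

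**3. Slope covariates**

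| | Covariates |
|---|---|
| In both lists (5) | age, baseline eGFR, diabetes, systolic pressure, ACE inhibitor/ARB |
| Section 7 only (2) | albumin excretion rate (AER), fibrosis stage |
| Section 9.2 only (4) | sex, CKD stage, albumin-to-creatinine ratio (ACR), cardiovascular history |

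Totals: 5 + 2 = 7 in Section 7 and 5 + 4 = 9 in Section 9.2. The albuminuria measure also differs elsewhere: the laboratory part of Section 8 names only the albumin excretion rate, while Section 9.2 goes on to use urinary protein and creatinine.

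**The case against.** The best defence is that a coherent schedule can be read from the protocol. Sections 5.4.3 and 6 together give visits at weeks 12 to 84 in steps of 12, and on that grid the CKD regression rule works as written. No single section states a 1-day or 4-week gap. Each appears only when the visit 7 label in the diet and activity records is joined to Section 6 or to a substudy sentence in Section 5.1. Figure 1 is not shown and may settle the overall schedule. This makes the 12-weekly grid the likeliest intention, but the conflicting labels remain in the text.

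A reader might go further on four points, and the documents do not support that:

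- *That no reading reaches 3 months.* Weeks 60 to 76 give 112 days, and 84 days is a nominal 3 months on a 12-weekly grid. The regression rule says 3 months; the at-least wording belongs to the CKD diagnosis.
- *That baseline CKD cannot be confirmed.* Nothing says that both values must come from visits 1 and 2, and earlier records could supply the first. What is missing is a named source.
- *That the slope must stop at week 72.* The final follow-up visit is not numbered. It may be visit 9, twelve weeks off drug, but a slope to last follow-up is a legitimate choice.
- *That loose confirmation favours curcumin.* In a blinded trial stratified by CKD, chance regression should arise in both arms. It would mainly raise both rates and blur the contrast.

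An SAP that is not shown may also fix one slope model. That would remove the choice in practice, but the two protocol sections would still disagree.

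**Conclusion.** Two internal contradictions stand. First, the confirmation interval for CKD regression is about 1, 28, 84 or 112 days depending on which sections are combined. It meets the protocol's 3 months only if visit 7 is at week 60, which assumes a 12-weekly grid with visit 3 at week 12. Second, one eGFR-slope analysis carries lists of 7 and 9 covariates with 5 in common, and the lists use different albuminuria measures.

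The unnamed source for the earlier baseline CKD value is a minor point, although it reaches beyond one outcome: CKD status is also a stratification factor (Section 5.5), an adjustment variable (9.2), and an imputation-matching and subgroup variable (9.5).

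The effect is on secondary kidney outcomes and the classification of CKD. The primary endpoint definition and the sample size do not change.

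**What to change.** 1. Restate every visit in study weeks and reconcile the labels in Sections 5.1, 6 and 8 with that schedule.
2. Define CKD regression on two named weeks about 3 months apart, for example weeks 60 and 72 if the 12-weekly grid is the intended schedule.
3. Keep one eGFR-slope covariate list, with one albuminuria measure, in both Section 7 and Section 9.2, fixed before unblinding.
4. State that the earlier of the two values defining baseline CKD comes from pre-trial records. Count in the regression denominator only patients whose CKD is confirmed that way. Patients left out keep the stratum in which they were randomised, and their number is reported by arm.

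The cost is protocol wording and retrieval of existing chart values, with no new visits or patients. The CKD-regression denominator may become slightly smaller.

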AE reporting and analysis

The reporting period for AEs will start at screening visit 1 and will continue until follow-up visit 8. SAEs were reported until day 504 (week 72) of the trial treatment and for 84 days post-EOT. All SAEs and adverse reactions will be evaluated by the investigators and recorded. The National Cancer Institute's common terminology criteria for AEs (CTCAE, V.4.02, 2010) will be used to grade each AE.

An AE will be deemed serious if it results in hospitalization or a visit to the emergency room where an intervention is made to avert hospitalization. The nature and number of all serious adverse events was adjudicated by an independent data management committee (DMC) who is unaware of treatment assignment at the time of ascertainment.

The central trial office (CRCTU, Turin) will keep detailed records of all AEs reported (nature, onset, duration, severity, outcome) and perform an evaluation with respect to seriousness, causality and expectedness.

Interim analysis of safety data will be performed and presented to the independent data management committee (DMC) on a 6-monthly basis. The unblinded DMC advises accordingly with regards to the trial conduct and specifically whether extra/new data monitoring will be required for the remainder of the trial.

The DMC operated in accordance with a trial specific charter based on a predefined template.

8. Analytical Methods

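### Seriousness is defined by hospital contact alone, so a fatal, life-threatening or disabling event outside hospital has no SAE or SUSAR status; the non-serious AE window and the SUSAR recipients also need correcting

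*Protocol*

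**What the plan says.** **Seriousness.** Section 7, AE reporting and analysis: "An AE will be deemed serious if it results in hospitalization or a visit to the emergency room where an intervention is made", where the purpose of the intervention is to avoid admission. The protocol gives no other criterion. The same subsection has the data management committee adjudicate all SAEs.

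**Deaths.** Section 7, Safety outcomes: "Selected events (including deaths, cardiovascular events, and acute pancreatitis) were adjudicated by an independent, external event-adjudication committee". This does not state that such events are SAEs.

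**Windows.** Section 7: "The reporting period for AEs will start at screening visit 1 and will continue until follow-up visit 8". The next sentence reads: "SAEs were reported until day 504 (week 72) of the trial treatment and for 84 days post-EOT".

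**Visits.** Section 6 lists "primary endpoint assessment including liver biopsy (visit 8, within 1 day of the EOT" and then "post-treatment follow-up assessment (visit 9, 12 weeks after EOT". Section 5.1, on the metabolic substudy, places visit 8 four weeks after treatment. The dietary and physical activity records in section 8 label visit 7 as end of treatment.

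**SUSARs.** Section 5.5 starts the SUSAR assessment from an SAE judged unexpected and at least possibly related to curcumin. It then states: "The latter will be reported to the MHRA and the NRES". Section 3 names two sites, both in Turin. Section 4 names one approving body, the San Luigi Gonzaga hospital Ethics Committee.

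**The concern.** Tolerability and safety are key secondary hypotheses (section 2), and safety is analysed descriptively (section 9.2). The safety conclusion is therefore only as good as the classification and capture of events.

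The seriousness definition is the gate to three later steps: SAE adjudication, the longer SAE window and SUSAR assessment. A definition tied to hospital contact keeps some of the gravest events out of all three. In a trial of 52 patients, one misclassified event could change the serious-event comparison visibly.

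Two further statements do not fit the rest of the protocol. The AE window closes at a visit called follow-up that section 6 places at end of treatment. The SUSAR recipients are not the body that approved the trial.

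**Working it through.** No error rate, power or sample size is involved. The check traces the rules and does calendar arithmetic.

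**1. Tracing an event without hospital contact.** Take a fatal event at home, with no admission and no emergency-room intervention.

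| Step | Rule | Result |
|---|---|---|
| Is it serious? | Section 7: admission, or emergency-room intervention to avert it | No |
| SAE adjudication by the data management committee? | Section 7: all SAEs | Not by this route |
| SUSAR assessment? | Section 5.5: begins from an SAE | Cannot enter |
| SAE window to 84 days after treatment? | Section 7: SAEs | Does not apply |
| Adjudicated as a selected event? | Section 7, Safety outcomes: deaths are included | Yes, but no SAE status or SUSAR duty is attached |

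A life-threatening or disabling event outside hospital fails the first four steps in the same way. It reaches the last only if it is one of the selected types.

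**2. The stated windows.** Inputs are 72 weeks of treatment and a 12-week post-treatment period.

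- 72 × 7 = 504 days, and 12 × 7 = 84 days. Both agree with section 7.
- 504 + 84 = 588 days, which is also when visit 9 falls. SAEs are therefore covered up to visit 9.

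**3. The gap for events not classed as serious.** Gap = 588 − day of visit 8.

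| Visit 8 timing | Day | Gap in days | Share of 588 |
|---|---|---|---|
| Section 6, at end of treatment | 504 | 84 | 84/588 = 14.3% |
| Section 6, one day later | 505 | 83 | 83/588 = 14.1% |
| Section 5.1, four weeks after treatment | 504 + 28 = 532 | 56 | 56/588 = 9.5% |

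Labelling visit 7 as end of treatment (section 8) does not by itself put visit 8 on any day. Combined with the three-month spacing of visits 7 and 8 in the CKD-regression definition (section 7), it would put visit 8 near 12 weeks after treatment and leave almost no gap. That combination conflicts with the visit list in section 6.

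**4. How the two rules combine.** Take a death at home eight weeks after treatment, at week 72 + 8 = 80, day 560. This is later than visit 8 at day 504, 505 or 532, so the AE window has closed. The event is not serious as defined, so the SAE window does not hold it either. Only the separate adjudication of deaths remains.

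**5. SUSAR recipients.** Neither body named in section 5.5 is the approving committee in section 4, and neither appears elsewhere in the protocol. Nothing sends SUSARs to the approving committee.

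**The case against.** **Deaths are still counted.** An independent, blinded committee adjudicates deaths, cardiovascular events and acute pancreatitis. This stands. A reader might infer that a death at home would go unreported, and the protocol does not support that. What is missing is its SAE and SUSAR status.

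**Serious events are followed past visit 8.** This stands too. A reader might infer that all adverse-event collection stops at visit 8, or that 14% of follow-up is unobserved. The sentence on SAEs rules that out. The gap concerns only events that the protocol does not class as serious.

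**Other provisions soften even that gap.** Adverse reactions are to be evaluated and recorded with no cut-off of their own. Every visit includes an interview, an examination and blood and urine chemistry, and a suspected AE prompts an unscheduled visit within 24 hours. Section 10.1 also lists case report forms for safety monitoring during follow-up. It would therefore be too strong to say that nothing non-serious is recorded after treatment. What ends at visit 8 is the formal reporting period.

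**The central office assesses seriousness and follows GCP.** It may in practice apply a wider test. But the only definition the protocol gives it is the hospital-based one, and a general reference to GCP does not replace an explicit rule.

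**The wrong SUSAR addressee loses no data.** Correct. The event stays in the trial database and in the six-monthly safety review. A reader might count this as a missed event, but it is a misdirected report.

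**Conclusion.** The main point holds. The seriousness definition is too narrow, and by the protocol's own rules it denies SAE and SUSAR status to fatal, life-threatening or disabling events without hospital contact. The protocol gives no frequency for such events, so the number affected is unknown.

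Two secondary corrections also hold. The formal window for non-serious AEs ends before the SAE window by 83 to 84 days (14.1% to 14.3% of 588) under section 6, or by 56 days (9.5%) under section 5.1. These figures assume visit 9 at day 588, and they stay uncertain until the visit 8 statements are reconciled. The SUSAR recipients do not match the approving body.

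No primary estimate, error rate or sample size is affected. The correction should be made because it is cheap and because safety is a stated hypothesis of the trial.

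**What to change.** 1. **Definition (section 7).** Extend it so that any AE that is fatal, life-threatening, disabling, a congenital anomaly or otherwise medically important is serious regardless of hospital contact. Keep the present hospital criteria. State that the deaths adjudicated under Safety outcomes are SAEs.
2. **AE window (sections 5.1, 6, 7 and 8).** Reconcile the timing and labels of visits 7, 8 and 9. Record all AEs through visit 9, in line with the 84-day period already used for SAEs.
3. **SUSAR recipients (section 5.5).** Name the approving ethics committee and the competent national authority. The protocol does not identify that authority, so the sponsor must supply its name.

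The cost is protocol wording plus AE recording at a visit that already takes place and already includes interview, examination and chemistry. If events have already been classified under the present rule, recorded AEs and adjudicated events should be re-read once against the wider definition.
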